9.4. Vital Signs, Body Weight and Height

Vital signs (blood pressure, pulse rate, respiratory rate, and body temperature), height, and weight will be assessed at the scheduled visits specified in Section 4.6.

A summary table of observed and change from baseline values will be provided at each scheduled visit for the enrolled population, from baseline at Month 3, Month 6, Month 9, and Month 12 and by each subgroup, ie, sex (male, female), ERT status (ERT naïve, ERT experienced), and overall if feasible for the enrolled population. By-visit summary will also include the last post-baseline values.

The incidence rates of PCS vital sign values and changes from baseline (Table 3), by parameter, will be summarized. The summary will indicate the number and percentage of subjects with PCS-low and PCS-high values at any time during treatment and will not be presented by visit.

A by-subject listing will be provided for each vital sign parameter.

Parameter	Baseline PCS Criterion	Post-Baseline PCS Criterion	
Heart Rate	≥100 bpm (high)	≥100 bpm and CFB ≥15 (high)	
Healt Rate	≤60 bpm (l ow)	≤60 bpm and CFB ≤-15 (low)	
Diastolic Blood Pressure	≥83 mmHg (high)	≥83 mmHg and CFB ≥15 (high)	
Diastolic Blood Pressure	≤64 mmHg (low)	≤64 mmHg and CFB ≤-15 (low)	
Svotolia Plaad Procesure	≥131 mmHg (high)	≥131 mmHg and CFB ≥20 (high)	
Systolic Blood Pressure	≤110 mmHg (low)	≤110 mmHg and CFB ≤-20 (low)	
Maight	NA	Percent CFB ≥7% (high)	
Weight		Percent CFB ≤-7% (low)	

Table 3. Vital Signs Potentially	Clinically Significant Values
----------------------------------	-------------------------------

*CFB = change from baseline

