7.2. Duration of Treatment

Subjects will continue on the study until the date of regulatory approval or marketing authorization for pediatric patients with Fabry disease and availability of reimbursed product in the participating subject's country, or study termination by Amicus. Since subjects will be entering this study as they complete Study AT1001-020, the duration of treatment will vary among subjects.

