9.2.4. Efficacy Assessments

9.2.4.1. Estimated Glomerular Filtration Rate

Estimated GFR will be calculated using the Schwartz formula according to the standards of the central laboratory. Subjects who reach the age of 18 and remain on study will continue to have eGFR calculated by this method by the sponsor at the time the value is entered into the database.

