3.1. Summary of Study Design

This is a long-term, open-label, uncontrolled, multicenter study to evaluate the safety, PD, and efficacy of migalastat treatment in subjects over 12 years of age with Fabry disease and with amenable GLA variants. Subjects will enroll in this study following completion of migalastat Study AT1001-020.

Enrollment in this study should immediately follow completion of Study AT1001-020 in order to maintain the continuity of treatment. As appropriate, assessments performed at the End of Treatment visit for Study AT1001-020 will be utilized for Visit 1 (baseline) assessments for this study.

In order to monitor safety, subsequent visits for this study were initially scheduled every 3 months with monthly interim telephone contacts. Following Amendment 2, the visit schedule was changed to every 6 months, with phone contacts at intervening 3-month intervals.

Subjects will remain on the same dose of migalastat that they were receiving in Study AT1001-020. If a subject's weight decreases to below 43 kg, an unscheduled visit will be arranged 2 to 4 weeks later in order to monitor the subject's weight.

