3.6. Study Procedures and Flowchart

Table 1 details the schedule of assessments:

Table 1. Schedule of Assessments

Assessments	Baseline ^a		Treatment Period					EOT/ ET	Follow- up		
Visit Interval	Day 1	Month 3 (TC)	Month 6	Month 9 (TC)	Month 12	Month 15 (TC)	Month 18	Month 21 (TC)	Month 24		30-Day Safety
Visit Window (days)	—	±6	±6	±6	±6	±6	±6	±6	±6	±6	±6
Informed consent/assent	х										
Inclusion/exclusion criteria	х										
Medical history	х										
Concomitant medications	х	Х	х	х	х	Х	Х	х	х	х	
Dosing diary ^b	х	\rightarrow	\rightarrow	\rightarrow	\rightarrow	\rightarrow	\rightarrow	\rightarrow	х		
FPHPQ questionnaire	х		х		Х		х		х	х	
PedsQL	х		х		Х		х		х	х	
Complete physical examination	х		х		Х		Х		Х	х	
Adverse events		Х	х	х	Х	х	Х	х	х	х	х
Vital signs (BP, HR, RR, Temp)	х		х		Х		Х		х	х	
Body weight	х		х		Х		х		х	х	
Height	Х		х		Х		Х		х	х	
Tanner Staging	х		х		Х		Х		х	х	
12-lead ECG	х		х		Х		Х		х	х	

Assessments	Baseline ^a		Treatment Period							EOT/ ET	Follow-up
Visit Interval	Day 1	Month 3 (TC)	Month 6	Month 9 (TC)	Month 12	Month 15 (TC)	Month 18	Month 21 (TC)	Month 24		30-Day Safety
Visit Window (days)	—	±6	±6	±6	±6	±6	±6	±6	±6	±6	+6
Chemistry (including eGFR using Schwartz formula)	х		х		Х		Х		Х	Х	
Hematology	х		х		х		х		х	х	
Plasma lyso-Gb ₃ , analogs, and exploratory PD biomarkers	Х		Х		х		х		х	Х	
Urinalysis (urine protein, albumin and microalbumin levels)	х		х		х		х		х	Х	
Urine pregnancy test or date of LMP (as applicable)°	х	х	Х	Х	Х	х	Х	х	Х	Х	X
Echocardiogram (LVMi and additional parameters)	х				Х				Х	Х	
Study treatment supply/resupply/ return	х		х		х		х		Х	Xd	

Table 1. Schedule of Assessments (Continued)

Abbreviations: BP = blood pressure; ECG = electrocardiogram; eGFR = estimated glomerular filtration rate; EOT = end of treatment; ET = early termination; FPHPQ = Fabry-Specific Pediatric Health and Pain Questionnaire; HR = heart rate; LMP = last menstrual period; LVMi = left ventricular mass index; lyso-Gb₃ = Globotriaosylsphingosine; PD = pharmacodynamic; PedsQL = Pediatric Quality of Life Inventory; RR = respiration rate; TC = telephone call; Temp = body temperature

Note: Following Month 24, visits will continue every 6 months with interim telephone contacts at 3-month intervals. The assessment schedule will repeat starting from Month 3. Note: For the purposes of this study, a month is considered to be 30 days.

^a End of study assessments from Study AT1001-020 will be used as baseline assessments for Study AT1001-036.

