5.5. Baseline Definition

For all safety, PD, and efficacy data, the baseline value is defined as the last non-missing measurement obtained on or before the administration of the first dose of study drug in Study AT1001-036 (Day 1).

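### The ±7% weight flag counts growth together with abnormal gain and rises with time on study, and SAP 9.7 commits to no within-subject Tanner table

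*SAP*

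**What the plan says.** **Weight flag.** In SAP 9.4, Table 3, the high limit for weight is "Percent CFB ≥7% (high" and the low limit is its mirror image. SAP 5.5 sets baseline as "the last non-missing measurement obtained on or before the administration of the first dose of study drug in Study AT1001-036 (Day 1"). A subject counts if the limit is ever met on treatment, and the count is not split by visit. Protocol 11.4.4.4 describes the vital-sign PCS counts in the same way. Weight is the only parameter in Table 3 with no absolute limit beside the change: heart rate and blood pressure need both.

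**Who is followed, and for how long.** Subjects are over 12. Protocol 9.2.4.1 provides for "Subjects who reach the age of 18 and remain on study". Protocol 7.2 says that "the duration of treatment will vary among subjects".

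**Change tables.** SAP 9.4 plans observed values and changes for weight and height at each scheduled visit, by sex and enzyme replacement status, plus the last post-baseline value. The same sentence names the visits as "from baseline at Month 3, Month 6, Month 9, and Month 12". It also says "height, and weight will be assessed at the scheduled visits specified in Section 4.6". In SAP 3.6, Months 3 and 9 are telephone contacts, and weight and height are measured at Months 6, 12, 18 and 24. After that, "Following Month 24, visits will continue every 6 months with interim telephone contacts at 3-month intervals". SAP 3.1 explains the mismatch: visits were 3-monthly at first, and "Following Amendment 2, the visit schedule was changed to every 6 months".

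**Tanner stage.** Protocol 11.1.1 and SAP 2.2.3 make change in Tanner stage a safety endpoint. SAP 9.7 plans a by-visit summary of results, the last post-baseline value and a listing. Protocol 11.4.4.5 asks only for descriptive statistics.

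**The concern.** Weight, height and Tanner stage are safety endpoints under the primary objective, long-term paediatric safety. Protocol 9.2.2.8 ties Tanner staging to the reversible infertility seen in male rats. The study has no control arm, so only an age and sex reference can show whether a gain exceeds what growth would produce, and the plan has none.

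An ever/never flag against a fixed starting weight in someone still growing is partly a clock. Ordinary gain crosses +7% if follow-up is long enough, while a true loss is measured from a weight the subject has outgrown. A reader of the clinical study report could take a high PCS-high count as a drug effect, or a low PCS-low count as reassurance, and neither would follow.

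For Tanner stage, a table of stage counts at each visit does not show who moved. How many subjects failed to progress is a within-subject question, and no planned table is committed to answering it.

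**Working it through.** The plan states no expected flag rate, so there is no figure to reproduce.

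**1. Steady gain that triggers PCS-high.** Inputs: the 7% limit (SAP Table 3); a 30-day month (SAP 3.6); 45 kg, the lower end of the weight range in the dose rationale (protocol 5.5), which is not a reported baseline of this study; 60 and 70 kg, which are assumed. Formula: kg/year = 0.07 × baseline weight ÷ years on study. The numerators are 3.15, 4.2 and 4.9 kg. Month 6 is 180 ÷ 365.25 = 0.493 years, and so on.

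| Followed to | Years | 45 kg | 60 kg | 70 kg |
|---|---|---|---|---|
| Month 6 | 0.493 | 6.4 | 8.5 | 9.9 |
| Month 12 | 0.986 | 3.2 | 4.3 | 5.0 |
| Month 18 | 1.478 | 2.1 | 2.8 | 3.3 |
| Month 24 | 1.971 | 1.6 | 2.1 | 2.5 |

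At every weight the bar falls 4-fold (1.971 ÷ 0.493 = 4.0) between Month 6 and Month 24. This needs no assumption about growth rates.

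**2. Share flagged, under assumptions only.** Take a 50-kg baseline and normally distributed gain rates. With mean 2 and SD 2 kg/year, 23% are flagged high at 1 year and 55% at 2 years. Over assumed means of 1 to 4 kg/year (SD 1.5 for mean 1, otherwise 2), the range is 5% to 60% at 1 year and 31% to 87% at 2 years. So wide a range says only that the count depends on growth and follow-up; it is not an estimate for this study.

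**3. PCS-low after growth.** If a subject has grown by a fraction x, the loss from current weight needed to reach -7% of the Day 1 value is (x + 0.07) ÷ (1 + x). For x = 0 it is 7.0%; for x = 0.07, 0.14 ÷ 1.07 = 13.1%; for x = 0.10, 0.17 ÷ 1.10 = 15.5%. From 45 kg, growth of 7% gives 48.15 kg and the flag needs 41.85 kg, a loss of 6.3 kg. That path passes below 43 kg, where SAP 3.1 and protocol 7.1 already arrange an extra weight visit. The cover is local: the -7% limit lies below 43 kg only for baselines under 43 ÷ 0.93 = 46.2 kg. From 60 kg the path is 64.2 to 55.8 kg (8.4 kg, 13.1%) and never comes near 43 kg.

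**4. Tanner tables.** SAP 9.3 and 9.5 name shift tables; 9.7 names none. SAP 5.1 offers change from baseline only where appropriate, which does not commit to it here. Assumed example with 10 subjects: baseline counts at stages 2/3/4/5 are 2/4/2/2 and last counts are 0/4/2/4.
- If everyone who moves rises one stage (two each of 2→3, 3→4 and 4→5), 2 of the 8 subjects below stage 5 do not progress.
- If both stage-2 subjects rise to 4 and both stage-4 subjects rise to 5, the four at stage 3 do not progress.

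The same table therefore fits 2 to 4 non-progressors, with no regression and no rise above two stages.

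**The case against.** The strongest reply is that nothing is lost. Raw weight and height change is tabulated by sex, every value is listed, and clinically significant examination changes are recorded as adverse events. A PCS count is a screen, and its ever/never form follows protocol 11.4.4.4. This stands. A reader might infer that the plan leaves weight safety unreadable; the documents do not support that. What remains is narrower: the PCS-high count alone cannot separate growth from a signal, and the raw change tables have no age and sex reference.

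The 45-kg case is the most easily triggered of the weights shown. At 70 kg to Month 12 the trigger is 5.0 kg/year, and subjects near adult size may hardly be affected. This also stands, and it limits the size of the effect but not its direction.

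The below-43-kg visit gives some cover for weight loss, so it would be wrong to infer that such losses go unnoticed. It is a conduct rule, not an analysis, and it helps only near that weight.

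The Section 4.6 reference might suggest that the visit schedule is undefined. It is not: the reference is a numbering slip for 3.6. Months 3 and 9 were also clinic visits before Amendment 2, so those data may exist and should not be dropped.

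On Tanner stage, the SAP matches the protocol's call for descriptive statistics, the listing allows non-progressors to be counted by hand, and by-visit tables by sex could narrow the range in the example above. All fair. A shift table is still the direct summary of a named change endpoint.

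**Conclusion.** The point holds as one of readability. The weight PCS-high count mixes expected growth with abnormal gain and rises with time on study; the triggering gain differs 4-fold between Month 6 and Month 24. PCS-low loses sensitivity as subjects grow: after 7% growth it takes a 13.1% loss from current weight. The tables in SAP 9.7 need not show within-subject Tanner progression.

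The formulas rest on the plan's own limits and 30-day month. The baseline weights are illustrative, and the share of subjects affected is unknown without growth rates.

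A reader might infer that a growth or puberty problem is suspected. The documents report none, and protocol 5.3.1 does not expect the fertility finding to add risk in children. The changes are worth making before database lock, but this is not a flaw that undermines the descriptive study.

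**What to change.** **SAP 9.4.**
- Keep the ±7% flag. Present the weight count by visit or with time on study (for example per patient-year; SAP 9.2 already derives that denominator), with a footnote that it is not adjusted for growth. Because protocol 11.4.4.4 describes counts that are not split by visit, record the change in SAP Section 12.
- Add changes in weight-for-age and height-for-age z-scores, by sex and exact age, from one growth reference named before database lock. Above its age range, report raw change only.
- Replace the Month 3 to Month 12 list with every nominal visit that has weight or height data. This includes Months 3 and 9 collected before Amendment 2, and Months 18, 24 and later.

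**SAP 9.7.** For each Tanner component and sex, add a shift table of baseline by last post-baseline stage. Give the number of subjects below stage 5 at baseline who had no increase, with their baseline age and time on study.

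**Cost.** No new assessments: all inputs are already collected. The work is modest programming and the choice of a single growth reference for a global study. Some shift-table cells will be small.

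**Outside this point.** The Section 4.6 reference is an editorial correction. The SAP also omits the protocol's age-group summaries without declaring it, and its Section 12 compares with Amendment 1 rather than Amendment 2. Both affect the whole SAP and should be raised separately.

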9.5. Electrocardiogram Results

A summary table of observed and change from baseline values in ECG results will be provided at each scheduled visit for the enrolled population. A summary table displaying shifts in interpretation from baseline to each assessment time-point, including the last post-baseline assessment, will be provided by sex (male, female), ERT status (ERT naïve, ERT experienced), and overall if feasible. By-visit summary will also include the last post-baseline values.

A by-subject listing will be provided, including each ECG parameter: heart rate (beats per minute [bpm]), PR interval [msec], QRS interval [msec], QT interval mean [msec], QTc (QTcF or QTcB) [msec] and interpretation. QTc=corrected QT interval, QTcF = corrected QT interval with Fridericia's formula, and QTcB = corrected QT interval with Bazett's formula.

9.6. Physical Examination

Complete physical examination, including HEENT (Head, Eyes, Ears, Neck and Throat), Respiratory, Cardiovascular, Dermatological, Lymph Nodes, Gastrointestinal, Neurological, Thyroid, Musculoskeletal and other assessments, will be conducted at baseline and each scheduled visit. A categorical summary table will be provided of the physical examination findings at each scheduled visit for the enrolled population by sex (male, female), ERT status (ERT naïve, ERT experienced), and overall if feasible. By-visit summary will also include the last post-baseline values.

A by-subject listing will be presented for each body system.

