11.4.4.5. Physical Examinations

Physical examination results will be presented for each body system/category examined; the number and percent of subjects judged to be normal, abnormal, or not performed will be summarized. Similarly, the results of the physical examinations will be summarized for subjects in the Safety Population who had an examination post baseline.

Tanner Stages will be summarized using descriptive statistics.

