2.2.3. Safety Endpoints

The safety endpoints of this study are as follows:

- incidence of treatment-emergent adverse events (TEAEs), serious adverse events (SAEs), and adverse events (AEs) leading to discontinuation of study drug
- change from baseline in clinical laboratory test results over time
- change from baseline in vital signs over time
- change from baseline in physical examination findings over time
- change from baseline in body weight and height over time
- change from baseline in electrocardiogram (ECG) results over time

- change from baseline in echocardiogram (ECHO) parameters from baseline to Month 12/ET
- change from baseline in Tanner stage

3. Study Design

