5.1. General Summary Table and Individual Subject Data Listing Considerations

Summary tables and listings will have text (eg, headers or footers) providing explanatory notes that cover, as appropriate: date of data extraction, date of output generation, Statistical Analysis System (SAS®) program name, and any other output-specific details that require further elaboration.

The descriptive summary statistics will be prepared for baseline, each visit, and change from baseline to each visit (if appropriate).

Row entries in post text tables are made only if data exist for at least one subject (eg, a row with all zeroes will not appear). The only exception to this rule applies to tables that summarize the study termination status of subjects (eg, reasons for not completing the study). In this case, zeroes will appear for study termination reasons that no subject satisfied. The summary tables will clearly indicate the number of subjects to which the data apply and data that is unknown or not performed will be distinguished from missing data. All data collected will be reported in data listings.

Missing dates will be imputed as described in Section 5.7. Missing AE severity and relationship will be imputed as described in Section 5.7.2. No other missing data imputation will be performed. When imputed or derived data are included in the individual subject data listings, they will be flagged.

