5.6.1.4. Change from Baseline

For any parameter at a specific visit, change from baseline is calculated as the value of the parameter at the specific visit minus the baseline value of that parameter, as defined above.

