9.3. Laboratory Evaluations

Clinical laboratory test values (hematology, serum chemistry, and urinalysis) and changes from baseline will be summarized by each visit and subgroup, ie, sex (male, female), ERT status (ERT naïve, ERT experienced), and overall if feasible for the enrolled population. By-visit summary will also include the last post-baseline values.

In addition, the following clinical summaries will be presented:

- Tables summarizing the frequencies and percentages of potential clinically significant (PCS; see Table 2) abnormalities at any time. The summary will indicate the number of subjects with PCS-low or PCS-high values at any time during treatment with migalastat but will not be presented by visit. PCS abnormalities will be determined both by investigator assessment and derivation from lab alert ranges provided by Amicus. PCS abnormalities that occur at unscheduled visits will be included.
- Tables displaying shifts from baseline to each assessment time-point, including the last postbaseline assessment, in laboratory test values from normal to high or low using normal range including eGFR, urine protein, and albumin.

Unscheduled visits will be included in PCS summaries and when determining the worst post-baseline assessment.

By-subject safety laboratory listings will be generated incorporating information and assessment results obtained from the designated laboratory which provided normal range and reported out of range flags. All laboratory results in Système International (SI) units will be presented in data listings. Tests will be listed in alphabetical order within their respective panels (hematology, serum chemistry, and urinalysis). Abnormal values will be flagged.

Chemistry		Hematology	
Alkaline Phosphatase	\geq 3 x Upper Limit Normal	II	$\leq 11.5 \text{ g/dL} \text{ (male)}$
AST	\geq 3 x Upper Limit Normal	Hemoglobin	\leq 9.5 g/dL (female)
ALT	\geq 3 x Upper Limit Normal	Hematocrit	$\leq 37\%$ (male)
BUN	\geq 30 mg/dL	петаюсти	$\leq 32\%$ (female)
Creatinine	$\geq 2.0 \text{ mg/dL}$	RBC count (absolute)	$<3.8 \ 10^{6}/uL \text{ or} > 5.5 \ 10^{6}/uL$
СРК	CPK $\geq 2 x$ Upper Limit Normal		$<4.5 \ 10^{3}/\text{uL} \text{ or } >13.5 \ 10^{3}/\text{uL}$
Gamma glutamyl transferase	$\geq 2 \text{ x Upper Limit Normal}$	Neutrophils	≤ 15%
Lactate dehydrogenase	\geq 300 U/L	Eosinophils	>0.7 10 ³ /uL
Glucose	\geq 100 mg/dL (fasting)	Platelet count	$\leq 75 \ 10^3/uL \text{ or } \geq 750 \ 10^3/uL$

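### Change from baseline in physical examination is a listed safety endpoint, but no planned table summarizes within-subject change

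*SAP*

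**What the plan says.** **Endpoint.** SAP 2.2.3 lists "change from baseline in physical examination findings over time" as a safety endpoint, and Protocol 11.1.1 uses the same wording. Long-term safety is the primary objective.

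**Planned displays.** SAP 9.6 states: "A categorical summary table will be provided of the physical examination findings at each scheduled visit". The table is split by sex and by prior enzyme replacement therapy, with an overall column if feasible, and includes the last post-baseline value. The section closes with: "A by-subject listing will be presented for each body system". SAP 9.6 does not name the categories. They come from Protocol 11.4.4.5, under which, for each body system, "the number and percent of subjects judged to be normal, abnormal, or not performed will be summarized". That section also plans a similar summary for subjects examined after baseline.

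**General rules.** SAP 5.1 says: "The descriptive summary statistics will be prepared for baseline, each visit, and change from baseline to each visit (if appropriate", with the closing qualifier in parentheses. SAP 5.6.1.4 says that "change from baseline is calculated as the value of the parameter at the specific visit minus the baseline value of that parameter".

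**Comparable data.** For laboratory values, SAP 9.3 plans "Tables displaying shifts from baseline to each assessment time-point". For ECGs, SAP 9.5 plans "A summary table displaying shifts in interpretation from baseline to each assessment time-point, including the last post-baseline assessment".

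**The concern.** The endpoint is defined within the subject: what each person's examination showed at baseline against what it shows later. The planned table is marginal: how many subjects fall in each category at each visit. For a continuous measure observed in the same subjects, the difference of the visit means equals the mean of the individual changes, so by-visit summaries still say something about average change. For a normal/abnormal finding they give only the net difference, and any number of new abnormalities can sit behind it if as many have resolved.

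At stake is whether a safety reader can see, from a table, how many subjects developed a new abnormality in a given body system. Baseline abnormalities are plausible here: Protocol 5.4 names skin findings among the common signs in children with Fabry disease, and skin is one of the systems examined. Offsetting movements are therefore possible in practice.

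**Working it through.** The documents give no figure on this point, so there is nothing to reproduce. The check has two parts.

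**1. Does any planned table or general rule supply the change summary?**

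- SAP 9.6 and Protocol 11.4.4.5: counts by category at each visit and at last post-baseline. Neither mentions a shift or a count of new abnormalities.
- SAP 5.1: calls for change from baseline only where appropriate. It does not say that physical examination qualifies, or what form the change would take.
- SAP 5.6.1.4: defines change as a subtraction. Abnormal minus normal has no value under that definition, so the rule does not produce a change variable for a category.
- SAP 9.3 and 9.5: where the authors wanted change in a categorical reading, they named a shift table. SAP 9.6 does not.
- SAP 12, which records departures from the protocol analysis, gives no reason for treating physical examination differently.

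A programmer following the text would produce by-visit counts and a listing, and no change table.

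**2. How far can by-visit counts leave the change undetermined?**

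Take one body system and N subjects examined at both baseline and a visit. Let b be the number abnormal at baseline, v the number abnormal at the visit, and x the number who were normal at baseline and abnormal at the visit.

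- Abnormal at both times = v − x. This cannot be below 0 or above b.
- Normal at both times = N − b − x. This cannot be below 0.
- Hence max(0, v − b) ≤ x ≤ min(v, N − b).
- Number resolved = b − (v − x). When b = v this equals x.

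The documents state neither a sample size nor a rate of abnormal examinations, so N, b and v below are assumptions.

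| N | b | v | Newly abnormal, lowest | Newly abnormal, highest | Highest as share of those normal at baseline |
|---|---|---|---|---|---|
| 20 | 5 | 5 | 0 | min(5, 15) = 5 | 5/15 = 33.3% |
| 10 | 3 | 3 | 0 | min(3, 7) = 3 | 3/7 = 42.9% |
| 20 | 6 | 6 | 0 | min(6, 14) = 6 | 6/14 = 42.9% |
| 30 | 9 | 9 | 0 | min(9, 21) = 9 | 9/21 = 42.9% |

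In each row the abnormal counts at baseline and at the visit are equal, and a table of those counts would look the same at both ends of the range. The upper end is a mathematical bound, reached only if every baseline abnormality resolves while the same number of other subjects become abnormal. It is not an estimate of what will happen.

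**The case against.** A reader might infer that the analysis does nothing but count, and that the endpoint is never measured. The documents do not support that. Examinations are scheduled at baseline and at every site visit. SAP 9.6 plans a listing by subject and body system, and SAP 13.2.5.3 sorts listings by subject and then by visit. Every new or resolved abnormality can be read there. The data exist and are displayed; the change is not tabulated.

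A reader might also infer that adverse event data pick up only changes judged clinically significant. Protocol 10.1.1 attaches that condition to its bullet on physical examination changes. Separate bullets cover new signs and conditions, and worsening of existing ones, without it. Many new findings would therefore enter the TEAE tables by system organ class and preferred term (SAP 9.2). What remains uncovered is mainly findings that are not reported as adverse events.

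A third inference is that drop-out would pass unseen. Subjects do leave at different times, but SAP 5.1 requires tables to show the number of subjects they describe, SAP 13.2.5.2 bases percentages on subjects with an observation unless otherwise noted, and the last post-baseline summary keeps the final examination of those who left. A shrinking denominator would show. None of this gives within-subject change, but the plan is not blind to attrition.

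Finally, table layouts are not among the documents, and SAP 9.6 says only that the table is categorical. A shift layout is not excluded; it is simply not called for. These objections narrow the point. They do not remove the mismatch between an endpoint worded as change and a table of by-visit counts.

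**Conclusion.** The point holds in a limited form: no planned table summarizes within-subject change in physical examination findings, although that change is a listed safety endpoint. The general rules do not fill the gap, and the SAP handles laboratory values and ECG interpretation differently without saying why. The endpoint as worded can be read only from the listings, or from the adverse event tables where a change was reported as an adverse event.

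The illustrative size, 0 to 5 newly abnormal subjects behind identical counts of 5 of 20, rests on assumed numbers, on the same subjects being examined at both times, and on the table taking the form the text describes.

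The consequence is small. The study is uncontrolled and reports summary statistics without hypothesis tests, physical examination is one of eight safety endpoints, and no decision rule in the documents depends on this table. This is a worthwhile improvement, not a flaw that undermines the study.

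**What to change.** Add to SAP 9.6, for each body system, a shift table with baseline status (normal, abnormal, not performed) in rows and the same categories in columns, at each scheduled visit and at last post-baseline. The ECG interpretation table in SAP 9.5 is the pattern.

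Optionally, add per body system the number and percentage of subjects normal at baseline who have any abnormality afterwards, and state whether examinations at unscheduled visits count.

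The cost is one further table (two with the option), programmed from data already collected and already due to be listed. No new assessment, visit or protocol procedure is needed.
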